5.2.8. Prior and Concomitant Surgery/Procedures

Procedures or surgeries that occurs prior to the first dose of study treatment are denoted “Prior”. Procedures or surgeries that occurs after first dose date but no later than 30 days after the last dose are denoted “Concomitant”.

Prior and concomitant surgery/ procedures will be classified using the MedDRA version 27.1.

The prior and concomitant surgery/procedures will be summarized by presenting the number and percentage of patients by PT and SOC. Patients having the same surgery/procedure multiple times will only be counted once for that PT or SOC. Each summary will be ordered by descending order of incidence of SOC according to total column and PT within each SOC. If the frequencies tie, an alphabetic order will be applied.

All prior and concomitant surgery/procedures will be presented a by-patient listing.

5.2.9. Efficacy Analyses

The safety analysis set will be used for PFS, and the response evaluable analysis set will be used for anti-tumor responses such as BOR, DoR, DCR, and TTR. No formal hypothesis testing is planned for this study. Two-sided 95% confidence intervals (CIs) will be calculated in the applicable summary, unless otherwise specified.

5.2.9.1. Secondary Efficacy Analyses

The number and percentage of patients in each category of derived BOR (CR, PR, Unconfirmed CR, Unconfirmed PR, MR, SD, PD, or NE) will be summarized by dose/disease cohorts for the response evaluable analysis set. ORR and ORR regardless of confirmation will be summarized by dose/disease cohorts. The two-sided 95% CIs of ORR and ORR regardless of confirmation will be calculated using the Clopper-Pearson method for each dose/disease cohorts.

The DCR will be analyzed in a similar way as ORR.

Tumor evaluation data will be presented in listings.

Swimmer plot will be presented for the treatment duration and tumor responses, including length of treatment duration, radiologic response, treatment ongoing or not, and death.

For the time to event endpoints, such as PFS and DoR, the median, 25% and 75% percentile of time-to-event will be estimated using Kaplan-Meier method with their corresponding 95% CI. For PFS, additionally, estimates will be provided for the PFS probability along with their 95% CIs which are calculated using linear transformation based on the method by Brookmeyer and Crowley (1982) at selected landmarks, for example, at 3, 6, 9, 12, and 18 months. The Kaplan-Meier plots will be

produced for PFS. The duration of follow-up will be calculated descriptively using the Kaplan-Meier method.

In order to assess duration of follow-up for PFS, Kaplan Meier estimates will be calculated in the same way as in their analysis, while using different censoring rule which reverses censoring indicator instead, i.e. patients who have event will be censored at the date of event. Patients who are censored will assigned as “event”.

Waterfall plot will be presented to depict the tumor shrinkage of target lesions, presenting each patient best percentage change in tumor size as a separate bar by dose/disease cohorts for the response evaluable analysis set. The best percentage change in target lesion size is defined as the maximum decrease or minimum increase among the percent changes from baseline to all post baseline visits per patient. In addition, spider plot will be presented including each patient percentage change in sum of target lesions, best overall response by dose/disease cohorts for the response evaluable analysis set. For both waterfall and spider plots, all the tumor assessment data from target lesion will be used up until the last evaluable prior to or on the date of (i) disease progression as defined by RECIST Version 1.1 (Eisenhauer et al., 2009) or RANO criteria for glioma patients, or death; or (ii) withdrawal of consent or lost to follow-up; or (iii) receiving subsequent anti-cancer medications, whichever is earlier.

5.2.10. Exposure of Study Treatment

Exposure of study treatment described in [Section 4.3](#) (duration of exposure, actual duration of exposure, cumulative dose, dose intensity, relative dose intensity) will be summarized by dose/disease cohorts and overall.

The following summary for dose modification will be summarized by dose/disease cohorts and overall.

- Number of patients with any dose modification (including both drug interruption and dose reduction)
- Number of patients with any drug interrupted (number of patients experienced drug interruption and reasons for drug interruption)
- Number of patients with any dose reduced (number of patients with any dose reduction and reasons for dose reduction)

5.2.11. Safety Analyses

Safety data during the treatment period will be summarized. Treatment period is defined as the duration from the date of the first study drug administration until 30+7 days (7-day window only applies to parameters collected by visit) or prior to the start of a subsequent anti-tumor therapy (whichever comes first) after last study drug administration.

5.2.11.1. Dose-Limiting Toxicity (DLT)

DLT analysis will be performed for the Part 1 based on the DLT evaluable analysis set.

In addition to summarizing number and percentage of patients with DLTs, DLTs will also be summarized by SOC, PT, and highest CTCAE grade.

DLTs will be listed.

5.2.11.2. Adverse Events

An overall summary of the number and percentage of patients along with the number of adverse events will be provided for the following categories of AEs:

- Any TEAE
- Any TEAEs by maximum CTCAE grade
- Any TEAE of CTCAE Grade 3 or higher
- Any TEAE Leading to Dose Modification
 - Any TEAE Leading to Dose Reduction
 - Any TEAE Leading to Drug Interruption
- Any TEAE Leading to Drug Discontinuation
- Any TEAE Leading to Death
- Any Treatment Related TEAE
- Any Treatment Related TEAE of CTCAE Grade 3 or higher
- Any Treatment Related TEAE Leading to Dose Modification
 - Any Treatment Related TEAE Leading to Dose Reduction
 - Any Treatment Related TEAE Leading to Drug Interruption
- Any Treatment Related TEAE Leading to Drug Discontinuation
- Any Treatment Related TEAE Leading to Death
- Any Serious TEAE
- Any Treatment Related Serious TEAE
- Any Special Interest TEAE (AESI)
- Any Treatment Related AESI
- Patients with Any COVID-19-related TEAEs as well as CTCAE Grade 3 or higher

The following categories will be summarized (the number and percent of patients) by SOC, PT and maximum CTCAE grade (Grade 1/2, Grade ≥ 3 , All Grade).

	Summary scope
TEAE	
• Any TEAE• TEAEs with CTCAE grade 3 or higher (maximum CTCAE grade by Grade 3, Grade 4, Grade 5)• TEAEs leading to dose modification
○ TEAEs leading to dose interruption○ TEAEs leading to dose reduction• TEAEs leading to discontinuation of study drug

	
 TEAEs leading to death (by SOC and PT only)
Treatment-related TEAE	
 Any treatment-related TEAE Treatment-related TEAEs with CTCAE grade 3 or higher (maximum CTCAE grade by Grade 3, Grade 4, Grade 5) Treatment-related TEAEs leading to dose modification 
 Treatment-related TEAEs leading to dose interruption Treatment-related TEAEs leading to dose reduction Treatment-related TEAEs leading to discontinuation of study drug Treatment-related TEAEs leading to death (by SOC and PT only)
Serious TEAE	
 All serious TEAE (Grade 1/2, Grade \geq3, All Grade, Related). Treatment-related serious TEAEs
COVID-19-related TEAEs	
 COVID-19-related TEAEs

In addition, all TEAE and treatment-related TEAE will also be summarized (the number and percent of patients) by PT and maximum CTCAE grade (All Grade, Grade \geq 3, Grade 1/2).

If a subject experienced the same adverse event (as identified by MedDRA preferred term) more than once during the study, the worst occurrence (e.g. worst grade) will be counted. Similarly, if a subject experienced more than one occurrence of the same SOC/PT, the worst occurrence (e.g. worst grade) will be counted within a particular SOC/PT. When summarizing AE by CTCAE grade, if a subject experienced more than one occurrence of the same SOC/PT, the worst severity grade will be counted. Each summary will be ordered by descending order of incidence of SOC and PT within each SOC. If the frequencies of SOC/PT tie, an alphabetic order of SOC/PT will be applied.

AESI Summary

AEs of special interest (AESI) are listed in the below table, and will be identified by MedDRA Query (SMQ)/PT:

AESI	Search Strategy
Abnormal hepatic function	Drug related hepatic disorders - comprehensive search (SMQ Code 20000006) Narrow search)

Abbreviations: AESI = adverse event of special interest; PT = preferred term; SMQ = standard MedDRA query.

All AESIs will be summarized in frequency and percent by AESI category, PT and maximum CTCAE grade (All Grade, Grade \geq 3, Grade 1/2). The followings will also be summarized for each AESI category:

- AESI
- Treatment Related AESI
- AESI of CTCAE Grade 3 or higher

- AESI meeting SAE criteria
- AESI leading to dose modification
- AESI leading to dose reduction
- AESI leading to dose interruption
- AESI leading to dose discontinuation
- AESI leading to death

Moreover, time to AESI onset (days), AESI duration (days) and AESI outcome (the number and percent of patients) will be summarized descriptively.

Time to AESI onset is defined as the time interval from the date of first dose of study drug to the earliest onset date among all AESIs. That is, if a subject has multiple AESI occurrences, the earliest AESI onset date will be used as the onset date to calculate time to onset of AESI.

AESI duration (days) will only be calculated for ended AESI as (AE end date-AE start date+1).

AE Listing

All AE will be listed. All AE information including AE term, start date, end date, severity, whether the AE is DLT, CTCAE grade, whether the AE is SAE, classification of SAE (if SAE), whether the AE is AESI, relationship to study drug, action taken, outcome, whether this event is considered as part of Differentiation Syndrome will be presented in subject data listings. If the AE is ongoing at the data cut-off date, it will be reported as 'Ongoing' in the listing.

In addition, separate listings of all SAEs, AESIs, AEs leading to death and AEs leading to discontinuation of study drug will be provided.

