8.2 Adverse Event Reporting

8.2.1 Adverse Event Reporting Period

After signing of the pre-screening informed consent, AEs due to the protocol-required intervention will be collected in the pre-screening phase.

After signing of the main study informed consent, all SAEs and AEs regardless of attribution will be collected until 30 days after the last dose of study drug or start of a new treatment of antitumor therapy, whichever is earlier. The relevant AEs will be followed up until they are recovered to the baseline status, already in a stable state as assessed by the investigator, start of new antitumor therapy, loss to follow-up, death, withdrawal of informed consent, the end of study, or it has been confirmed that the AEs are unrelated to the study drug. After this period, the investigators should report only SAEs that are considered to be related to the study drug.

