4.4.1. Adverse Events (AEs)

All AEs will be coded from verbatim text to preferred term (PTs) and grouped by system organ class (SOC) using the Medical Dictionary for Regulatory Activities (MedDRA) version 27.1. AEs will be graded by investigator according to NCI CTCAE v5.0. Missing severity grade will not be imputed.

An AE is considered a TEAE:

(i) If one of the criteria is met:

1. If the onset date is on or after the start of study treatment until 30 days after the last dose or prior to the start of a subsequent anti-tumor therapy (whichever comes first), or if the onset date is missing; or
2. If the AE has an onset date before the start of study treatment, but worsened in severity after the study drug administration (i.e. SAE start date is on or after the start of study treatment until 30 days after the last dose or prior to the start of a subsequent anti-tumor therapy (whichever comes first));

(ii) Beyond 30 days after the last dose or after the start of a subsequent anti-tumor therapy (whichever comes first), treatment-related SAEs will also be considered as TEAEs.

Investigator assessed AEs causality to study drug will be classified as "Related" and "Not Related". An AE with a missing causality will be classified as "Related" to study drug.

Other AE variables include drug-related AEs, COVID-19 related AEs, AEs leading to study drug modifications (i.e. dose interruption, dose reduction, or study drug withdrawal), AEs leading to death, and SAEs.

For AEs which are not on-going, duration of AE (days) is defined as AE end date – AE start date +1; for on-going AEs, the end date will be listed as ‘Ongoing’.

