5.1.2.1. Adverse Events Start/End Date

AEs with onset/end dates that are partially/completely missing will be imputed as follows.

(i) AE start date:

- If the AE onset date is completely missing, the AE start date will be imputed as the reference start date;
- If the AE onset date is partial missing, then
 - If both the year and the month are available and the year and the month are the corresponding year and month of the reference start date, then the AE start date will be imputed as the reference start date;
 - If both the year and the month are available and the year and the month are not equal to the corresponding year and month of the reference start date, then the AE start date will be imputed as the 1st day of the month;
 - If only the year is available and the available year is the corresponding year of the reference start date, then the AE start date will be imputed as the reference start date;
 - If only the year is available, and the available year is not equal to the corresponding year of the reference start date, then the AE start date will be imputed as the January 1st of the year

(ii) AE end date will be imputed as below for the partial date only, the imputation rules only apply when the AE is not ongoing:

- If both the year and the month are available, AE end date will be imputed as the last day of the month;
- If only the year is available, AE end date will be imputed as the December 31st of the year.

If the imputed AE end date is after the death date for patients is know to be dead at end of study or cut off date, the date of the death will be used for AE end date. If the imputed AE end date is after the last known alive date for patients alive at the end of study or cut off date, the date of last known alive date will be use for AE end date.

For AE continuing at the cut-off date, the end date will not be imputed and instead will be reported as “ongoing”.

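### AESI duration is summarised for ended events only, so it is biased short whenever some hepatic AESIs are still ongoing

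*SAP*

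**What the plan says.** SAP 5.2.11.2 defines one AESI category, abnormal hepatic function, identified by the narrow search of a standardised MedDRA query ("Drug related hepatic disorders - comprehensive search"). For that category it plans: "Moreover, time to AESI onset (days), AESI duration (days) and AESI outcome (the number and percent of patients) will be summarized descriptively". Duration has a restriction: "AESI duration (days) will only be calculated for ended AESI as (AE end date-AE start date+1").

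The rest of the SAP is consistent with that restriction. Section 4.4.1 applies it to all adverse events: "For AEs which are not on-going, duration of AE (days) is defined as AE end date" minus start date plus one. Section 5.1.2.1 adds: "For AE continuing at the cut-off date, the end date will not be imputed"; the event is simply shown as ongoing. No censoring date is assigned anywhere, and no other analysis brings open events back into a duration statistic.

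By contrast, SAP 5.1.1 sets Kaplan-Meier as the method for time-to-event variables, and 5.2.9.1 uses it for PFS and duration of response. AESI duration is not treated that way, and no reason is given.

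Protocol 8.2.1 follows relevant events to recovery or stability. It also allows follow-up to stop at "start of new antitumor therapy, loss to follow-up, death, withdrawal of informed consent, the end of study". Protocol 6.1.21 lets the study end 1 year after the last subject's first visit.

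**The concern.** Duration of an adverse event is a right-censored quantity: for an event still open, we know only that it has lasted at least as long as it was observed. Removing open events and summarising the remainder is a complete-case analysis in which the chance of being complete falls as the duration rises. If observation time after onset is unrelated to how long the event would last, ended events are on average shorter than all events, and the mean and median are biased downward.

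Open events are plausible here. Patients have advanced cancer, and follow-up can stop at new therapy, death or study end. A hepatic abnormality that becomes stable without returning to baseline may never receive an end date.

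At stake is how the clinical study report describes the reversibility of the one toxicity singled out for special attention, which is also a listed potential risk in Protocol Table 3. A reader who takes the duration row as typical time to recovery would be misled to the extent that events remain open.

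**Working it through.** The documents give no expected AESI duration, AESI rate or share ongoing, so there is no planned figure to reproduce. The effect of the rule is illustrated under stated assumptions.

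**Inputs from the documents.** Duration is end date minus start date plus 1, for ended events only (SAP 5.2.11.2). Ongoing events have no end date (SAP 5.1.2.1).

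**Assumptions.** Durations are exponential with true mean m, so the true median is m × ln 2. Each event is observed for a fixed C days after onset. The values of m and C are mine.

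**Formulas.**
- Share ongoing: q = exp(−C/m)
- Ended-only mean: m − C·q/(1 − q)
- Ended-only median: −m·ln(1 − 0.5(1 − q))

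**Example, m = 28 and C = 30.** q = exp(−30/28) = 0.343. Ended-only mean = 28 − 30 × 0.343/0.657 = 12.4 days. Ended-only median = −28 × ln(1 − 0.5 × 0.657) = 11.2 days, against a true median of 28 × ln 2 = 19.4 days.

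| m = 28; C (days) | Ongoing | Ended-only mean (true 28) | Ended-only median (true 19.4) |
|---|---|---|---|
| 30 | 34.3% | 12.4 (−56%) | 11.2 (−42%) |
| 60 | 11.7% | 20.0 (−28%) | 16.3 (−16%) |
| 90 | 4.0% | 24.2 (−13%) | 18.3 (−6%) |
| 180 | 0.2% | 27.7 (−1%) | 19.4 (about 0%) |

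**Slower resolution.** Writing M for the true median, the share ended is F = 1 − 0.5^(C/M), and the ended-only median is −M·log2(1 − F/2).
- M = 42, C = 60: F = 0.629, ended-only median 22.9 days; 42/22.9 = 1.8-fold understatement.
- M = 42, C = 37: F = 0.457, 15.7 days; 42/15.7 = 2.7-fold.
- M = 84, C = 60: F = 0.390, 26.3 days; 84/26.3 = 3.2-fold.

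The 37 and 60 days are assumed observation times from onset. The SAP's 30+7-day window (4.1.3) runs from the last dose and is a different quantity.

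**Random censoring.** With independent exponential censoring and a share f ongoing, the ended-only mean is m(1 − f). For m = 28 this is 28 × 0.90 = 25.2, 28 × 0.75 = 21.0 and 28 × 0.60 = 16.8 days at f = 10%, 25% and 40%. A simulation of 1,000,000 events at each f gave the same means, and ended-only medians of 17.5, 14.6 and 11.6 days. Ongoing events had true means of 53.5, 49.1 and 44.7 days, so they are longer on average. Even so, 17%, 19% and 22% of them were shorter than the overall true median. Keeping the ongoing events as censored observations gave an estimated mean of 28.0 days in all three cases.

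**The case against.** The strongest reply is that the exclusion affects one statistic only and is openly stated. Ongoing AESIs remain in the summaries by preferred term and maximum grade, in the Grade 3 or higher, "AESI meeting SAE criteria", dose modification, discontinuation and death rows, in time to onset, and in the outcome summary, which has no ended-only limit. The listings mark them as ongoing. Continuous summaries carry n (SAP 5.1.1), so a shortfall against the AESI event count can be found. All of this stands, and it limits the harm. It does not correct the duration figure, and no planned table sets the number unresolved beside it.

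Follow-up is also meant to continue to recovery or stability (Protocol 8.2.1, 8.3.5), and for drug-related events and SAEs to resolution (Protocol 6.1.20). The share ongoing could therefore be near zero, and the bias with it. That stands too.

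Three stronger readings are tempting, and the documents support none of them:
- A reader might infer that the excluded events are the longest and most serious. They are longer on average, but some are short. Nothing links being unresolved to grade or seriousness; an open event may be mild or recent.
- A reader might infer that the rule always shortens the reported duration. With no ongoing AESI it does nothing.
- A reader might infer that dose selection rests on this figure. Protocol 4.1.1 names MTD, safety, PK and PD as considerations for RP2D, without naming AESI duration. The Safety Review Committee decides during escalation (SAP 6.1). The final analysis follows database lock (SAP 6.3), and the study did not proceed to expansion (SAP 1).

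A plain Kaplan-Meier analysis of every AESI record would have faults of its own. Censoring at death treats a fatal case as one that could still resolve. Repeat events within a patient are not independent. A grade change opens a new eCRF entry (Protocol 8.7.3), so one episode can appear as several records. With about 27 to 36 subjects over eight dose levels (27/8 = 3.4 to 36/8 = 4.5 per level), medians by dose level would mean little. The fix has to deal with each of these.

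**Conclusion.** The point holds as a reporting bias in one descriptive safety statistic. The direction is predictable: the duration is too short whenever AESIs are ongoing, provided observation time after onset is not tied to the event's length. The size is unknown because the share ongoing is not given. At an assumed true mean of 28 days, the median is understated by between about 0% and 42%. It is understated about 2- to 3-fold if true medians are 42 to 84 days with 37 to 60 days of follow-up. All of these figures rest on exponential durations and chosen inputs; they are illustrations, not predictions. The consequence is a possibly misleading figure in the study report, not a wrong dose decision. The change is still worth making: it follows the SAP's own rule for time-to-event variables and needs no new data.

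**What to change.** 1. Relabel the current row 'duration among resolved AESIs' and print the number of ongoing AESIs beside it.
2. Add a Kaplan-Meier summary of time to resolution, pooled across dose levels, using each patient's first AESI episode.
3. Define the episode: merge linked eCRF entries that record only a change of grade.
4. Censor episodes still ongoing at the last adverse event assessment or the data cut-off. Treat death with an unresolved AESI as a competing event: count the patient as not resolved, keep the patient in the denominator, and report these deaths separately.
5. Give the median with its 95% CI, and show it as 'not reached' where that applies.

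The cost is a short addition to SAP 5.2.11.2 and one extra table, with some programming to link entries into episodes. The reported duration will be longer and, with few events, less precise. If only one change is made, step 1 removes most of the risk of misreading.

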5.2.11.3. Death

Number of deaths and primary cause of death are summarized descriptively. Similarly, the deaths happening during the treatment period and follow-up period will also be tabulated.

Data of deaths will be provided as patient list in which the on-treatment death will be flagged.

5.2.11.4. Laboratory Evaluations

For selected quantitative laboratory test, the observed values and change from baseline will be summarized by scheduled visit using descriptive statistics. For selected qualitative laboratory test, number and percentage of patients with categorical results will be summarized for each scheduled visit. Toxicities for clinical labs will be characterized according to NCI CTCAE, v5.0 ([Appendix 1](#) shift in grade from baseline to the worst post-baseline value will be summarized. Both the scheduled and unscheduled assessments will be used to identify the worst post-baseline values.

Shift table from baseline to worst post-baseline value according to abnormality (Normal / Abnormal, Not Clinically Significant / Abnormal, Clinically Significant) assessed by investigator will be provided.

The number and percentage of patients satisfying abnormal hepatic laboratory values categories defined in Section 4.4.2 will be summarized.

The frequency and percentage of patients with categories of abnormal hepatic laboratory values during the treatment period will be summarized.

Listings of all laboratory data with normal reference ranges, and CTCAE grades (when possible) will be provided.

